4.3. Exclusion Criteria

Subjects who meet *any* of the following exclusion criteria are not to be enrolled in this study.

- 1) BMI < 18
- 2) Prior exposure to an direct-acting antiviral targeting HCV NS5B (all cohorts) or HCV NS5A (Cohort 3 only)
- 3) Prior null response to PEG+RBV therapy (Cohorts 1 and 2) or for patients with cirrhosis, prior treatment failure with IFN-based therapy not resulting from treatment intolerance (Cohort 3)
- 4) Male with pregnant female partner (Cohorts 1 and 2 only)
- 5) Chronic liver disease of a non-HCV etiology (e.g., hemochromatosis, Wilson's disease, alpha-1 antitrypsin deficiency, cholangitis)
- 6) Infection with hepatitis B virus (HBV) or human immunodeficiency virus (HIV)
- 7) Unstable psychiatric condition
- 8) Significant cardiac disease including or resulting in:
 - a) Cardiomyopathy
 - b) Left ventricular ejection fraction $\leq 50\%$
 - c) Hospital admission for myocardial infarction, heart failure within 1 year of Screening
 - d) Pulmonary hypertension within 1 year of Screening
- 9) Clinically significant abnormality on ECG at Screening, including a QTcF > 500 msec, or > 450 msec in patients who concomitantly use methadone.

- 10) History of clinically significant hemoglobinopathy (Cohorts 1 and 2 only)
- 11) History of porphyria (Cohorts 1 and 2 only)
- 12) Malignancy within the 5 years prior to screening, with the exception of specific cancers that are cured by surgical resection (basal cell skin cancer, etc). Subjects under evaluation for possible malignancy are not eligible.
- 13) Chronic use of systemically administered immunosuppressive agents (e.g., prednisone equivalent > 10 mg/day)
- 14) Clinically-relevant drug or alcohol abuse within 12 months of Screening
- 15) Current or prior history of clinical hepatic decompensation (e.g., ascites, jaundice, encephalopathy or variceal hemorrhage)
- 16) History of clinically-significant illness or any other major medical disorder that may interfere with subject treatment, assessment or compliance with the protocol
- 17) History of a primary gastrointestinal disorder (or post operative condition) that could interfere with the absorption of the study drug
- 18) Excessive alcohol ingestion, defined as > 3 glasses/day (1 glass is equivalent to: beer [284 mL], wine [125 mL], or distilled spirits [25 mL]) for females and > 4 glasses/day for males)
- 19) Inability to collect blood for safety, PK, and efficacy throughout the study

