- 20) Donation or loss of more than 400 mL blood within 2 months prior to Day 1
- 21) Use of any prohibited concomitant medications as described in Section 5.8 within 21 days of the Day 1 visit
- 22) Known hypersensitivity to RBV (Cohorts 1 and 2 only), the study investigational medicinal product, the metabolites, or formulation excipients
- 23) Receipt of any investigational product within a time period equal to 10 half-lives of the product, if known, or a minimum of 4 weeks prior to study drug administration
- 24) Subjects with hepatocellular carcinoma (HCC) are excluded from the study. In cirrhotic patients, liver imaging (e.g., ultrasound) within 6 months of Day 1 is required to exclude hepatocellular carcinoma (HCC)

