5.8. Concomitant Medications

Concomitant medications taken within 30 days of Screening, up to and including the date of the visit four weeks after discontinuation of study treatment, need to be recorded in the source documents and eCRFs.

5.8.1. Cohorts 1 and 2

The following medications are prohibited from 21 days prior to the Day 1 visit through the end of treatment:

- Drugs disallowed per prescribing information of RBV (COPEGUS®)
- Concomitant use of certain medications or herbal/natural supplements (inducers of drug transporters i.e. P-gp) with study drug(s) may result in pharmacokinetic interactions resulting in decreases in exposure of study drug(s). Representative medications which are excluded from 21 days prior to Day 1 through the end of treatment are listed below:

Drug	Agents Disallowed	Concomitant use with study drug may potentially result in changes of study drug concentration as listed below
Anticonvulsants	Phenobarbital, Phenytoin, Carbamazepine, Oxcarbazepine	Decrease in concentration of study drug
Antimycobacterials	Rifampin, rifabutin, rifapentine	Decrease in concentration of study drug
Herbal/Natural Supplements	St. John's Wort, Echinacea, Milk thistle (i.e., silymarin), Chinese herb sho-saiko-to (or Xiao-Shai-Hu-Tang)	Decrease in concentration of study drug
Other	Modafinil	Decrease in concentration of study drug

5.8.2. Cohort 3

Concomitant use of certain medications or herbal/natural supplements (inhibitors or inducers of drug transporters ie, P-gp) with study drug(s) may result in PK interactions resulting in increases or decreases in exposure of study drug(s). The use of amiodarone is prohibited from **60 days prior to Baseline/Day 1** through the end of treatment. Examples of representative medications which are prohibited from 21 days prior to Baseline/Day 1 through the end of treatment are listed below:

Table 5-1. Disallowed and Concomitant Medications to be Used with Caution

Drug Class	Agents Disallowed	Use with Caution
Acid Reducing Agents ^a		Proton-Pump Inhibitors, H2-Receptor Antagonists, Antacids
Antiarrhythmics ^b		Quinidine
Anticonvulsants ^c	Phenobarbital, Phenytoin, Carbamazepine, Oxcarbazepine	
Antimycobacterials ^c	Rifabutin, Rifapentine, Rifampin	
Cardiac Medications ^b	Amiodarone ^e	Digoxin
Herbal/Natural Supplements ^c	St. John's Wort, Echinacea, Milk thistle (i.e., silymarin), Chinese herb sho-saiko-to (or Xiao-Shai-Hu-Tang)	
HMG-CoA Reductase Inhibitors ^d	Rosuvastatin	Pravastatin, Pitavastatin

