- a It is recommended to separate antacid and LDV/SOF administration by 4 hours. H2-receptor antagonists may be administered simultaneously with or staggered from LDV/SOF at a dose that does not exceed doses comparable to famotidine 40 mg twice daily. Proton-pump inhibitor doses comparable to omeprazole 20 mg can be administered simultaneously with LDV/SOF. Proton-pump inhibitors should not be taken before LDV/SOF.
- b May result in an increase in the concentration of study drugs and/or concomitant medications. Coadministration of LDV/SOF with digoxin may increase the concentration of digoxin. Caution is warranted and therapeutic concentration monitoring of digoxin is recommended when coadministered with LDV/SOF.
- c May result in a decrease in the concentrations of study drugs.
- d Use with study drugs may result in an increase in the concentration of the HMG-CoA Reductase Inhibitors. Monitor for signs and symptoms of muscle weakness or myopathy, including rhabdomyolysis.
- e May result in symptomatic bradycardia. Mechanism is not currently known. The use of amiodarone is prohibited from **60 days prior to Baseline/Day 1** through the end of treatment.

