6.2. Pretreatment Assessments

6.2.1. Screening Visit

Prospective subjects should be screened within 42 days prior to first dose on Day 1. If the subject does not begin the treatment phase within this 42-day window, all screening evaluation procedures must be repeated. No more than one repeat screen visit is allowed for each subject, unless prior written approval has been provided by the Sponsor.

Written informed consent must be obtained from each subject before initiation of any screening procedure. After a subject has provided informed consent, the investigator and other study personnel will determine if the subject is eligible for participation in the study. This assessment will include a review of the inclusion/exclusion criteria and completion of all screening procedures as outlined in [Table 6-1](#) and [Table 6-2](#).

Once eligibility is confirmed, the study site will complete an eligibility worksheet for each screened subject and submit for Sponsor review. The sponsor will assign a unique subject number for each eligible subject and provide the subject number information to the site prior to Day 1 visit.

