6.2.2. Medical History

Medical history including details regarding illnesses and allergies, date(s) of onset, and whether condition(s) is currently ongoing, and medication history will be collected on all subjects during screening. Information related to HCV infection will be collected. In addition, a cirrhosis determination will be made as follows:

Cirrhosis determination

- Cirrhosis is defined as any one of the following:
 - Liver biopsy showing cirrhosis
 - Fibroscan (in countries where locally approved) showing cirrhosis or results > 12.5 kPa within 6 months of Day 1
 - FibroTest® score of > 0.75 AND an AST:platelet (APRI) ratio of > 2 during Screening
- Absence of cirrhosis is defined as any one of the following:
 - Liver biopsy within 2 years of Screening showing absence of cirrhosis
 - Fibroscan (in countries where locally approved) with a result of ≤ 12.5 kPa within ≤ 6 months of Day 1
 - FibroTest® score of ≤ 0.48 AND APRI of ≤ 1 during Screening

In the absence of a definitive diagnosis of presence or absence of cirrhosis by the above criteria, a liver biopsy is required.

In addition, a determination of cardiac function will be made as follows:

- Echocardiogram demonstrating left ventricular ejection fraction > 50% performed prior to Day 1 visit. Enrollment allowed based on local read of study if central read is not available.

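### Exclusion 21 sets a 21-day window for every drug prohibited in Section 5.8, but Section 5.8.2 bars amiodarone in Cohort 3 from 60 days before Day 1

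*Protocol*

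**What the plan says.** Exclusion 21 in Protocol Section 4.3 bars "Use of any prohibited concomitant medications as described in Section 5.8 within 21 days of the Day 1 visit". It names neither a drug nor a cohort.

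Section 5.8.2, which covers Cohort 3, sets two periods. The first is for amiodarone alone: "The use of amiodarone is prohibited from 60 days prior to Baseline/Day 1 through the end of treatment". The next sentence gives 21 days for the representative drugs in Table 5-1. Amiodarone is also in that table, with a footnote that restores the longer period and gives the reason: "May result in symptomatic bradycardia. Mechanism is not currently known. The use of amiodarone is prohibited from 60 days prior to Baseline/Day 1". Section 5.8.1, for Cohorts 1 and 2, uses 21 days and does not name amiodarone.

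Four other provisions bear on whether a case would be noticed:

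- Section 6.2.1 sets the screening window: "Prospective subjects should be screened within 42 days prior to first dose on Day 1". It also says that "the study site will complete an eligibility worksheet for each screened subject and submit for Sponsor review".
- Section 5.8 sets what must be recorded, starting with "Concomitant medications taken within 30 days of Screening".
- Section 6.2.2 says that "medication history will be collected on all subjects during screening", with no stated lookback.
- Exclusion 9 bars a "Clinically significant abnormality on ECG at Screening", and exclusion 8 bars significant cardiac disease.

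**The concern.** Sites decide eligibility from the numbered criteria. The criterion for prohibited medication gives a shorter period than the protocol's own safety rule for one drug in one cohort. The longer period guards against a cardiac reaction whose mechanism the protocol says is unknown. A site that works through Section 4.3 alone could therefore pass a candidate whom Section 5.8.2 excludes.

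Detection after dosing is a weak substitute. In the Cohort 3 schedule, the first ECG after Day 1 is at Week 4. Vital signs, including pulse, are taken from Week 1, but by then the subject has already been dosed.

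**Working it through.** The plan states no figure to reproduce. The check compares the two rules and then counts days.

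**Inputs**

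- Exclusion 21: 21 days before Day 1 (Section 4.3).
- Amiodarone, Cohort 3: 60 days before Day 1 (Section 5.8.2 and Table 5-1, footnote e).
- Screening: at most 42 days before Day 1 (Section 6.2.1).
- Required medication recording: from 30 days before Screening (Section 5.8).

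Convention: a last dose exactly on the boundary day counts as barred under each rule.

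**1. Does the cross-reference import the 60 days?** No. Exclusion 21 uses Section 5.8 to say which drugs count, then states its own period. Had it stopped at the reference, the longer period would have carried over. No other exclusion criterion names amiodarone or a 60-day washout. The protocol does adapt its criteria by cohort elsewhere (exclusions 2, 3, 4, 10, 11 and 22), so the lack of an adaptation here looks like an omission.

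**2. The gap, by last amiodarone dose in Cohort 3**

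| Last dose, days before Day 1 | Exclusion 21 | Section 5.8.2 |
|---|---|---|
| 0 to 21 | barred | barred |
| 22 to 60 | not barred | barred |
| 61 or more | not barred | not barred |

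Length of the gap: 60 − 21 = 39 days.

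**3. Does required recording reach back far enough?** With Screening *s* days before Day 1 (1 ≤ *s* ≤ 42), covering the full 60 days needs a lookback of 60 − *s* days before Screening.

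| *s* | Lookback needed (60 − *s*) | Covered by 30 days? |
|---|---|---|
| 1 | 59 | no |
| 14 | 46 | no |
| 30 | 30 | yes |
| 42 | 18 | yes |

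The condition 60 − *s* ≤ 30 gives *s* ≥ 30. Required recording covers the full period only when Screening is at least 30 days before Day 1. A question about the 60 days before Screening is always enough, since 60 ≥ 60 − *s*.

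**4. Who cannot clear 60 days from a given Screening visit?** A candidate who stopped *x* days before Screening is at most *x* + 42 days from the last dose on Day 1. With day 60 barred, the candidate needs *x* + 42 > 60, so *x* ≥ 19. Anyone who stopped less than 19 days before Screening cannot qualify within that 42-day window.

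**The case against.** The strongest reply is that the two rules do not collide. Exclusion 21 can be read as a minimum and Section 5.8.2 as a stricter rule for one drug, and a site can obey both. The 60 days appears twice in the very section to which exclusion 21 sends the reader. Section 5.8.2 itself has a 21-day general statement, with a footnote that overrides it for amiodarone. The sponsor also reviews each eligibility worksheet before it assigns a subject number. This largely stands: a reader might infer that the protocol permits enrolment of recent amiodarone users, and it does not. What remains is that the criterion, applied as worded, passes a candidate whom another section bars. A worksheet checked against the 21 days in Section 4.3 may not show the problem.

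A second reply is that the 30-day rule governs what must be recorded and does not limit what an investigator may ask. Section 6.2.2 also requires a medication history, and Screening one day before Day 1 is unrealistic given the worksheet step. This is fair. The history may close the gap, but nothing says that it must reach back far enough.

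Third, exclusions 8 and 9 remove many candidates at cardiac risk. They lower the risk, but neither sets an amiodarone washout.

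A reader might also infer that such cases would go unreported, because they are not eligibility deviations under exclusion 21. The documents do not support that. For the SAP's listing of eligibility deviations they give only a title. A breach would still be a deviation from Section 5.8.2. It could appear in the major protocol deviation summary (SAP Section 4.3) if classed as major. Any amiodarone that was recorded would appear in the prior and concomitant medication listing (SAP Section 7.3; Listing 16.2.4.4).

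**Conclusion.** The point holds as a minor internal inconsistency, and exclusion 21 is wrong as written for amiodarone in Cohort 3. The gap is 39 days (last dose 22 to 60 days before Day 1), on the convention that day 60 is barred. If a last dose on day 60 were allowed, the gap would be 38 days and the threshold in step 4 would be 18 days instead of 19.

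The number of subjects affected is unknown and probably small: Cohort 3 plans 15 subjects, and the documents give no rate of amiodarone use. No estimate of bradycardia risk is possible from them.

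Nothing suggests that anyone chose 21 days for amiodarone, so this should not be read as a design decision. It does not touch Cohorts 1 and 2, where Section 5.8.1 names no amiodarone rule. It has no bearing on the sample size, the SVR12 analysis or any other statistical method.

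**What to change.** Amend the end of exclusion 21 to read: *within 21 days of the Day 1 visit (60 days for amiodarone, Cohort 3)*. At Screening, ask about amiodarone use over the preceding 60 days. An amiodarone exception in the sentence that introduces Table 5-1 would be optional tidying.

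The cost is one phrase in an amendment and one history question, with no added procedure or routine visit. A candidate who stopped amiodarone less than 19 days before Screening would have to be screened again. Section 6.2.1 allows one repeat screen without prior written sponsor approval. Section 5.8.2 already implies that burden, so the amendment does not create it.

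The documents do not say whether Cohort 3 enrolment is complete. If it is, the sponsor can still check medication histories against the 60-day rule and record any breach as a deviation from Section 5.8.2.

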5. INVESTIGATIONAL MEDICINAL PRODUCTS

5.1. Sofosbuvir (SOF)

5.1.1. Formulation

SOF tablets, 100 mg, are yellow, round, film-coated, plain-faced tablets.

SOF tablets, 400 mg, are yellow, capsule-shaped, film-coated tablets debossed with “GSI” on one side and “7977” on the other side.

In addition to the active ingredient, SOF tablets contain the following inactive ingredients: mannitol, microcrystalline cellulose, croscarmellose sodium, colloidal silicon dioxide, magnesium stearate, polyvinyl alcohol, titanium dioxide, macrogol, talc, and yellow iron oxide.

5.1.2. Packaging and Labeling

SOF tablets, 100 mg, are packaged in white, high density polyethylene (HDPE) bottles. Each bottle contains 28 tablets and polyester packing material. Each bottle is enclosed with a white, continuous thread, child-resistant screw cap with an induction-sealed, aluminum-faced liner.

SOF tablets, 400 mg, are packaged in white, high density polyethylene (HDPE) bottles. Each bottle contains either 28 or 30 tablets and a silica gel desiccant canister or sachet and polyester packing material. Each bottle is enclosed with a white, continuous thread, child-resistant screw cap with an induction-sealed, aluminum-faced liner.

SOF bottles to be distributed to centers in the US and other countries shall be labeled to meet all applicable requirements of the US Food and Drug Administration (FDA) and Annex 13 of Good Manufacturing Practices: Manufacture of investigational medicinal products (February 2010) and/or other local regulations as applicable.

5.1.3. Storage and Handling

SOF bottles should be stored at a controlled room temperature until required for administration. Controlled room temperature is defined as 25 °C (77 °F); excursions are permitted between 15 °C and 30 °C (59 °F to 86 °F).

All drug products should be stored in a securely locked area, accessible only to authorized site personnel. To ensure the stability of the study drug and to ensure proper product identification, the drug product should not be stored in a container other than the container in which they are supplied. Consideration should be given to handling, preparation, and disposal through measures that minimize drug contact with the body. Appropriate precautions should be followed to avoid direct eye contact or exposure through inhalation when handling SOF.

Sufficient quantities of SOF tablets to complete the entire study will be shipped to the investigator or qualified designee from Gilead Sciences Clinical Supply Management (or its designee).

5.1.4. Sofosbuvir (SOF) Dosage and Administration

SOF will be administered as 200 mg or 400 mg po daily. SOF (100 mg or 400 mg) tablets will be supplied by Gilead Sciences for all subjects.

5.2. Ribavirin (RBV)

5.2.1. Formulation

RBV tablets, 200 mg, are blue, capsule-shaped, film-coated tablets debossed with “3RP” on one side and “200” on the other side. In addition to the active ingredient, RBV tablets contain the following inactive ingredients: microcrystalline cellulose, lactose monohydrate, croscarmellose sodium, povidone, magnesium stearate, polyvinyl alcohol, titanium dioxide, macrogol, talc, FD&C blue #2.

5.2.2. Packaging and Labeling

The RBV tablets are packaged in white, HDPE bottles. Each bottle contains 168 tablets and rayon coil packing material and is enclosed with a white, continuous thread, child-resistant screw cap with an induction-sealed, aluminum-faced liner.

RBV bottles to be distributed to centers in the US and other countries shall be labeled to meet all applicable requirements of the US Food and Drug Administration (FDA) and Annex 13 of Good Manufacturing Practices: Manufacture of investigational medicinal products (February 2013) and/or other local regulations as applicable.

5.2.3. Storage and Handling

RBV tablets should be stored at 25 °C (77 °F); excursions are permitted between 15 and 30 °C (59 and 86 °F).

All drug products should be stored in a securely locked area, accessible only to authorized site personnel. To ensure the stability of the study drug and to ensure proper product identification, the drug product should not be stored in a container other than the container in which they are supplied. Consideration should be given to handling, preparation, and disposal through measures that minimize drug contact with the body. Appropriate precautions should be followed to avoid direct eye contact or exposure through inhalation when handling RBV.

5.2.4. RBV Dosage and Administration

RBV will be administered as 200 mg po daily. RBV should be dosed with food and with SOF to maximize adherence. RBV dose may be managed at the discretion of the Investigator in communication with the Medical Monitor.

RBV tablets (200 mg) will be supplied by Gilead Sciences for all subjects.

5.3. Co-administration of Sofosbuvir (SOF) and Ribavirin (RBV)

Each subject will be given instructions to maintain approximately the same daily dosing interval between study drug doses.

If a subject forgets to take the medication at the correct time, it may be taken later in the day; however, no more than 400 mg dose of SOF should be taken on any calendar day. The subject should resume the standing dosing schedule on the next day. Study medications should not be cut or split. No food restrictions apply to SOF; however, SOF should be taken with RBV and with food for optimal adherence.

On the day of clinic visits, subjects will be instructed to take their study medication on the day prior to clinic visits, 20-28 hours before the administration of the study medication at the clinic. Subjects should bring their medication with them to the clinic and take their study medication after all pre-dose assessments are completed.

5.4. Ledipasvir/ Sofosbuvir (LDV/SOF)

5.4.1. Formulation

Ledipasvir 90mg/ sofosbuvir 400mg fixed dose combination (FDC) tablets are orange, diamond-shaped, film-coated tablets containing 400 mg of SOF and 90 mg of LDV. The tablets are debossed with “GSI” on one side and “7985” on the other side. The LDV/SOF (90mg/400mg) tablets contain the following inactive ingredients: lactose monohydrate, copovidone, microcrystalline cellulose, croscarmellose sodium, colloidal silicon dioxide, magnesium stearate, polyvinyl alcohol, titanium dioxide, talc, polyethylene glycol, FD&C yellow # 6 /sunset yellow FCF aluminium lake.

5.4.2. Packaging and Labeling

Ledipasvir 90 mg/ sofosbuvir 400 mg tablets are packaged in white, high density polyethylene (HDPE) bottles. Each bottle will contain 30 tablets, a silica gel desiccant and polyester packing material. Each bottle is enclosed with a white, continuous thread, child-resistant screw cap with an induction-sealed, aluminum-faced liner.

LDV/SOF bottles to be distributed to centers in the US and other countries shall be labeled to meet all applicable requirements of the US Food and Drug Administration (FDA) and Annex 13 of Good Manufacturing Practices: Manufacture of investigational medicinal products (February 2010) and/or other local regulations as applicable.

